4.4.4.3 Laboratory variables analysis

Not applicable.

4.4.4 Analysis of vital sign variables

Not applicable.

4.4.4.5 Analysis of other safety variables

Not applicable.

4.4.4.6 Analysis of pharmacokinetic and pharmacodynamic variables

Not applicable.

4.4.4.7 Analysis of health economics variables

Not applicable.

4.4.5 Discontinuation Tracking

A listing for subject disposition and a table with summary of disposition will be provided. In the disposition summary table, early withdrawal at time points that are defined by each interim analysis will also be summarized. The programmatic thresholds for these time point are defined as below, and the target dates for these interim time points are defined in Table 1:

- Early withdrawal < Month 13: it includes subjects who discontinued before Month 13 (- 2 weeks);
- Early withdrawal < Year 2: it includes subjects who discontinued before Year 2 (- 4 weeks);
- Early withdrawal < Year 3: it includes subjects who discontinued before Year 3 (- 4 weeks);
- Early withdrawal < Year 4: it includes subjects who discontinued before Year 4 (- 4 weeks).

A subcategorization of CRF-defined discontinuation reasons will be further classified based on comments provided at a subject's exit. A listing and a summary table will be provided.

4.4.6 Interim analyses

Interim analyses will be conducted on all study variables at 4 time points:

- Following completion of all subjects Month 13 follow-up visits;
- Following completion of all subjects Year 2 follow-up visits;
- Following completion of all subjects Year 3 follow-up visits; and
- Following completion of all subjects Year 4 follow-up visits.

For these interim analyses, AEs and concomitant medications that started on or before the study visit will be included. If the study visit was not conducted, events/medications that started on or before the scheduled study day + 4 weeks (2 weeks for Month 13) will be included.

5.0 Data Handling Conventions

5.1 Baseline and Follow-Up Visits

Visits and time points for all analyses will be as recorded on the eCRFs. Baseline will be the last non-missing values from the Visit 1 (Day 1)/Baseline visit scheduled to occur prior to receiving study treatment. Unscheduled visit will not be used for analysis purposes in this study.

5.2 Missing Data

5.2.1 Missing AEI data due to subject discontinuation

If a subject discontinues the study before 2 or 5 years without an adverse event of interest, the subject will be assumed to have no adverse events of interest between the date of discontinuation and the 2 or 5-year time point when conducting the formal hypothesis testing. A sensitivity analysis will be conducted using the multiple imputation method to impute an outcome for these subjects.

To better determine covariates that will be used to conduct multiple imputation for missing event, the subjects who remain in the study or have had an event of interest will be compared to those who drop out without any injection site nodules and/or papules (or any AEI other than injection site nodules and/or papules), with respect to baseline characteristics and number of injection sessions to assess if missing appears to be missing at random or missing completely at random. Baseline characteristics include demographics (age, gender, ethnicity and race), Fitzpatrick skin type and medical history. Continuous factors include age and number of injection sessions. Age will be compared using a two sample t-test. Number of injection sessions will be compared using a wilcoxon rank sum test, as the data is highly discrete. Categorical factors will be compared using Pearson's Chi-square test, with Fisher's exact test as an alternative when the cell counts are less than 5.

A listing of discontinuation reasons for subjects who discontinued without an injection site nodule and/or papule or any AEI other than injection site nodule and/or papule will be provided, to detail the reason for missing.

5.2.2 Rules for imputing stop dates for adverse event, subject reported event, and prior/concomitant therapy

The imputed stop date will be derived from the CRF event/therapy stop date. If the CRF stop date day, month, and year are not missing then the imputed stop date will equal the CRF stop date. If any part of the CRF stop date is missing, the following rules will be utilized to impute the stop date.

- If the event/therapy is ongoing, the stop date will be set to missing.
- Otherwise, if the year is missing, a) if the subject is still in the study and the study is ongoing, the event will be assumed to be ongoing, and stop date will be set to missing; b) if the subject has left the study, the stop date will be set to the subject's final study date.
- If the year is present and the month is missing, the stop date will be set to the minimum of the last day of the given year and the subject's final study date if the subject has left the study, and it will be set to the last day of the given year otherwise.

• If the year and month are both present, the stop date will be set to the minimum of the last day of the given month for the given year and the subject's final study date if the subject has left the study, and it will be set to the last day of the given month otherwise.

If the imputed stop date is non-missing and prior to the imputed start date, the imputed stop date will be set to the imputed start date.

5.2.3 Rules for imputing start dates for adverse event, subject reported event, and prior/concomitant therapy

The imputed start date will be derived from the CRF event/therapy start date. If the CRF start date day, month, and year are not missing then the imputed start date will equal the CRF start date. If any part of the CRF start date is missing, the following rules will be utilized to impute the start date.

- If the year is missing, the start date will be imputed as the minimum of the Study First Treatment Date and the imputed stop date.
- If the year and month are both present and are not the same as the year and month of the Study First Treatment Date, the start date will be set to the first day of the given month for the given year.
- If the year and month are both present and are the same as the year and month for both the Study First Treatment Date and the imputed stop date, the start date will be set to the minimum of the Study First Treatment Date and the imputed stop date.
- If the year and month are both present and are the same as the year and month of the Study First Treatment Date but not that of the stop date, the start date will be set to the date of Study First Treatment.
- If the month is missing but the year is present and is not the same as the year of the Study First Treatment, the start date will be set to January 1st of the given year.
- If the month is missing but the year is present and is the same as the year for both the Study First Treatment Date and the imputed stop date, the start date will be set to the minimum of the Study First Treatment Date and the imputed stop date.
- If the month is missing but the year is present and is the same as the year of the Study First Treatment Date but not that of the stop date, the start date will be set to the date of first treatment.

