Interim analyses are planned following completion of all subjects' Month 13, Year 2, 3, and 4 follow-up visits. All safety and efficacy data up to the interim cut- off date will be cleaned, interim locked, analyzed and reported. Formal hypothesis testing will be performed at Year 2 and 5. The adjustment for type I error for the primary hypothesis is not necessary, since no change to the study such as early termination is planned after the interim analysis.

Missing data

The following rules will be applied to handle missing data in the safety analyses:

- If a subject discontinues the study before 5 years, all his/her safety information before discontinuation will be used in the safety analysis and no imputation of missing data between the date of discontinuation and the 5-year time point will be made. Sensitivity analyses for primary and secondary hypotheses will be conducted.
- If the timing of an adverse event cannot be identified because of missing data and the subject is treated, the adverse event will be considered as a treatment- emergent adverse event (TEAE).
- If the assessment of the intensity is missing, the most severe case will be assumed in the frequency tables of adverse event intensity.

CONFIDENTIAL

	If the assessment of the relationship to the Sculptra® Aesthetic or injection procedure is missing, a possible relationship to the Sculptra® Aesthetic will be assumed in the frequency tables of possibly related adverse events. Detailed plans for handling missing data will be contained in the statistical analysis plan.
Duration of Study Period	The study participation for each subject will be approximately 5 years in duration. Subjects will receive open-label treatment at their screening/initial treatment visit (Visit 1, Day 1 – first injection session). Subjects will continue to receive open-label treatment for up to 9 weeks (Visit 2, Week 3 [second injection session]; Visit 3, Week 6 [third injection session]; and Visit 4, Week 9 [fourth injection session]) if needed and determined by the clinical trial Investigator. Subjects will continue with follow-up visits at Months 3, 6, 9, and 13, and Years 2, 3, 4, and 5.

FLOW CHART OF STUDY PROCEDURES 2

Table 1 - Flow Chart 1 - Overview of Study Procedures

Study Phase:	Screening/	Addition	al Treatment	(if needed)	Follow-Up							
	Initial Tx	(3	Week Interv	als)	(All times Relative to the INITIAL Treatment Visit, Day 1)							

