Subjects treated with Sculptra® Aesthetic and Cosmoplast during the controlled phase showed a consistent, progressive, and significant improvement over baseline for the primary variable WAS beginning 3 weeks after the last treatment. Though the treatment effect of Sculptra® Aesthetic was maintained for up to 13 months, the Cosmoplast treatment effect returned to baseline within 3 months of the final treatment.

Commonly occurring short-term injection-related site reactions were reported in both treatment groups. In this clinical study the percentage of subjects with nodules and/or papules was greater after Sculptra® Aesthetic (17.2% [20 of 116]) than after the control treatment (12.8% [15 of 117]). This reflects 8 Sculptra® Aesthetic subjects who experienced nodules, 10 Sculptra® Aesthetic subjects who experienced papules, and 2 Sculptra® Aesthetic subjects who experienced both nodules and papules. After the first Sculptra® Aesthetic injection session, time to onset for nodules was 160 days (median) and 209 days (mean), and for papules, time to onset was 55 days (median) and 159 days (mean). After Sculptra® Aesthetic injection, the duration of nodules was 100 days (median) and 180 (mean) days, and for papules, was 110 days (median) and 176 days (mean). One subject with a papule required a single intralesional corticosteroid injection and the event resolved. For 3 subjects with nodules/papules, no information on outcome was available at the end of the 25-month extension phase study. For all remaining subjects, nodules/papules resolved spontaneously. None of these events were reported as a serious adverse event by the investigator. Table 3 shows adverse event data that were collected from patient diaries over the controlled phase (0 to 13 months Sculptra® Aesthetic versus Cosmoplast).

CONFIDENTIAL

Table 3 - Intensity of adverse events after the initial treatment session, recorded in the 14 day subject diary (Controlled Phase) - All-Treated Population

SCULPTRA Aesthetic (First Treatment Session: N = 116)						Cosmoplast (First Treatment Session: N = 117)						
		Severity of A	dverse Eve	nt ^a			Severity of Adverse Event ^a					
Injection Procedure Related Event	Total subjects reporting symptoms ^a n (%)	Mild n	Moderate n	Severe n	Missing n	Total subjects reporting symptoms ^a n (%)	Mild n	Moderate n	Severe n	Missing n		
Localized Swelling	94 (81.0)	64	24	5	1	76 (65.0)	60	13	1	2		
Localized Tenderness	94 (81.0)	63	24	2	5	83 (70.9)	62	16	1	4		

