Average time of duration:	Nodules	180 days
	Papules	176 days

[figure not shown]
*one subject reported mild injection site pain approximately 20 months after first injection, no information on outcome was available at the end of the 25 month extension phase study

Most side effects were mild and resolved on their own. Five new Sculptra® Aesthetic - related events were reported more than 13 months after first injection with Sculptra® Aesthetic in 3 subjects: 2 papules (1.9%), 1 nodule (0.9%) and 2 injection site pain (0.9%).

Study subjects who had received Sculptra® Aesthetic in the controlled phase of the study were additionally followed for safety and efficacy at Months 19 and 25 after the last injection session.

During the long-term surveillance phase, the Sculptra® Aesthetic group continued to demonstrate statistically significant improvements over baseline in WAS. The effect depended on baseline WAS (see Figure 1).

Figure 1 - Wrinkle assessment scores throughout Study DL6049-0301

TS4 = Pre-treatment session 4 (9 weeks after initial treatment)

Wk3 = 3 weeks after last treatment session

Mth 3, 6, 9, 13, 19, 25 = 3, 6, 9, 13, 19, 25 months after last treatment session

Source: Sculptra® Aesthetic package insert

The experience with Sculptra® Aesthetic in immune-competent subjects with darker skin types (ie, Fitzpatrick types¹⁸ IV-VI [see Appendix I]), was limited in the above study (ie, 22 out of 116 subjects treated with Sculptra® Aesthetic had skin type IV-VI). Thus, the Sponsor has committed to perform this postapproval study (PAS) to assess the safety of Sculptra® Aesthetic on at least 100 evaluable subjects with Fitzpatrick skin type IV-VI (including at least 15 with Fitzpatrick skin type IV and 85 with Fitzpatrick skin type types V or VI) up to 5 years (ie, completion of the follow-up phase). This PAS, in conjunction with the above pivotal study, would provide significant information to confirm the safety of Sculptra® Aesthetic in darker skin types over a longer period of observation and to assess device-related long-term incidence of chronic inflammation.

For detailed information regarding the efficacy and safety of Sculptra® Aesthetic, please refer to the Sculptra® Aesthetic package insert.

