13.7 MISSING DATA

The following rules will be applied to handle missing data in the safety analyses:

- If a subject discontinues the study before 5 years, all his/her safety information before discontinuation will be used in the safety analysis, and the subject will be assumed to have no adverse events between the date of discontinuation and the 5-year timepoint. Sensitivity analyses for primary and secondary hypotheses will be conducted as described in Section 13.5.4.1.
- If the timing of an adverse event cannot be identified because of missing data and the subject is treated, the adverse event will be considered as a TEAE.
- If the assessment of the intensity is missing, the most severe case will be assumed in the frequency tables of adverse event intensity.
- If the assessment of the relationship to the Sculptra® Aesthetic or injection procedure is missing, a possible relationship to the Sculptra® Aesthetic will be assumed in the frequency tables of possibly related adverse events.

Detailed plans for handling missing data will be contained in the statistical analysis plan.

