		4. Update the number of sets that will be imputed.	
		5. Update the algorithm used for multiple imputation.	
		6. Remove standard errors or CI from imputation estimates.	

	Section 5.4: Add section to clarify how duration and time to onset are calculated.
	Section 6.0: Add a deviation for the MI modeling.

Table of Contents

SIGNATURE PAGE	

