4.3.2 Safety populations

The analysis population for safety will include the ITT population and the PP population. The ITT population is the primary population for hypothesis testing. The Completer2 and Completer5 populations will be used for sensitivity analyses of the primary and secondary hypotheses.

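### The formal 2- and 5-year analyses count dropouts without an event as event-free for time nobody observed, so the incidences are understated, including both co-primaries

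*SAP*

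**What the plan says.** Both co-primary endpoints are percentages of subjects with an event over 5 years: nodule and/or papule, and any other AEI. The 2-year versions are secondary (SAP 4.2.2.1). The primary population for testing is ITT, meaning everyone with at least one injection (SAP 4.3 and 4.3.2).

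For a subject who discontinues without an AEI, SAP 5.2.1 states that in the formal tests "the subject will be assumed to have no adverse events of interest between the date of discontinuation and the 2 or 5-year time point". Protocol 13.7 has the same rule: "the subject will be assumed to have no adverse events between the date of discontinuation and the 5-year timepoint". The Protocol synopsis words it differently: "no imputation of missing data between the date of discontinuation and the 5-year time point will be made". With a full ITT denominator the two wordings give the same count.

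The plan also has other analyses of the same outcome:

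- SAP 5.2.1: "A sensitivity analysis will be conducted using the multiple imputation method to impute an outcome for these subjects".
- SAP 4.3.2: "The Completer2 and Completer5 populations will be used for sensitivity analyses of the primary and secondary hypotheses".
- SAP 4.4.4.2: Kaplan-Meier estimates of time to first occurrence, listed among the other adverse event analyses.

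The SAP document history for version 2.0 includes this entry for Section 5.2.1: "Remove standard errors or CI from imputation estimates".

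**The concern.** Adverse events are collected up to exit through visits, monthly contacts and the early-termination visit. What is lost is any first event after exit. Under the rule such an event counts as absent while the subject still counts in the denominator. The numerator can therefore be too low but never too high. The shortfall is zero only if no dropout would have had a later first event.

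Long-term incidence is the main product of this post-approval study, and under this rule poorer retention makes the device look safer. The hypotheses are blacked out. If they compare incidence with an upper limit, the error favours the device.

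Late onset is documented. Protocol Section 4 says of the pivotal study that "related events were reported more than 13 months after first injection", and these included two papules and one nodule. That study ended at 25 months, so it says nothing about Years 3 to 5.

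**Working it through.** **Attrition implied by the plan.** Protocol 7.1 gives 863 enrolled for 604 evaluable. 604/0.70 = 862.9, rounded up to 863. The skin-type minima follow the same rule: 15/0.70 = 21.4, rounded up to 22, and 85/0.70 = 121.4, rounded up to 122. The implied loss is 1 − 604/863 = 30.0% by Year 5.

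**Inputs from Protocol Section 4.** Nodules/papules occurred in 20/116 = 17.2%. Mean onset was 209 days for nodules and 159 days for papules. At most 3 of the 20 affected subjects had a new nodule or papule after Month 13, so at least 17/20 = 85% had onset by then.

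**Assumptions.** Dropout is independent of AEI. Steady dropout is exponential with 30% lost by Day 1826, so the daily rate is −ln(0.70)/1826. That gives 7.5% lost by Day 397 and 13.3% by Day 731. The alternative puts half of the 30% before Day 397.

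**Formula.** Expected reported incidence = p × (mean, over the onset times of affected subjects, of the probability of still being in follow-up).

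**Illustrative test.** One-sided 2.5%, exact binomial, n = 863, with an upper limit equal to the true rate. At 17.2% the test rejects with 126 events or fewer, an attained level of 2.2%. The last column is the chance of declaring the rate below the limit when it is not.

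| 5-year nodule/papule scenario | True | Reported | Shortfall (points) | Error |
|---|---|---|---|---|
| Exponential onset, mean 159–209 days; steady dropout | 17.2% | 16.7–16.5% | 0.5–0.7 | 5–7% |
| Same onset; half of dropout before Month 13 | 17.2% | 16.2–16.0% | 1.0–1.2 | 10–14% |
| Heavier late tail (Weibull shape 0.25); steady dropout | 17.2% | 16.2% | 1.0 | 12% |
| 17.2% by Month 25 plus 2 points over Month 25 to Year 5; steady dropout | 19.2% | 18.2% | 1.0 | 10% |
| Constant 5-year hazard; steady dropout | 17.2% | 14.5% | 2.7 | 54% |

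Exponential onset with these means puts 85–92% of onsets by Month 13, in line with the pivotal timing. The constant-hazard row does not fit that timing and is an upper scenario only. It has a closed form: with h = −ln(1 − 0.172)/1826 and c = −ln(0.70)/1826, reported = h/(h + c) × [1 − exp(−(h + c) × 1826)] = 14.5%. In the fourth row, the first 17.2 points yield 16.64 and the late 2 points yield 1.56, together 18.2.

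**Second co-primary.** No rate or onset time is given. Under a constant hazard, an assumed true 10% is reported as 8.4% and an assumed 5% as 4.2%.

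**2-year endpoint.** With 13.3% lost by Day 731, a true 17.2% is reported as 16.6–16.7% with pivotal onset and 16.1% with a constant 2-year hazard.

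**Kaplan-Meier check.** In 4,000 simulated trials of 863, comparing the upper 97.5% log-log limit of 1 minus Kaplan-Meier with 17.2% gave an error of 2.2% (constant hazard) and 2.4% (exponential onset, mean 184 days).

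**The case against.** The strongest reply is that the plan already holds a remedy. If dropout is independent of AEI, the Completer5 proportion is unbiased for 5-year incidence, with about 604 subjects and an ordinary binomial interval. This is correct, and the remaining question is which estimate is tested. The tested one is the biased one. Completer5 also discards the events of subjects who left.

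Several limits stand:

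- The hypotheses, alpha and limit are blacked out, as is the list of sensitivity analyses. A bounding analysis may exist there. The error rates above are illustrations only.
- The absence of standard errors and intervals on the imputation estimates is known only from the document history, because the current imputation text is not fully visible.
- The 17.2% is itself a crude all-treated proportion. The late percentages in Protocol Section 4 (2 papules as 1.9%, 1 nodule as 0.9%) imply a denominator of about 106–108 rather than 116. If the hidden limit came from that figure, a Kaplan-Meier estimate set against it would not be like for like.
- The 30% is inferred and applies to Year 5. The 2-year loss would be smaller.
- After a death, assuming no later event is correct, and censoring would slightly overstate incidence.
- With pivotal onset and steady dropout, the shortfall is about half of the 1.3-point standard error at n = 863.

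These points limit the claimed impact. They do not remove the downward bias from the tested figure.

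**Conclusion.** The concern holds and should be fixed. The rule is explicit, governs the formal tests, and biases both co-primary incidences downward. The direction follows from the rule itself, whatever the blacked-out hypotheses say. The size depends on assumptions: 30% loss by Year 5, dropout independent of AEI, and the onset patterns shown. For nodules/papules the shortfall is probably about 0.5 to 1.2 points. It would be larger if subjects leave because a reaction is emerging and has not been recorded. For the second co-primary the size cannot be established from the documents. The effect on the test decision is conditional on an upper-limit comparison.

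**What to change.** In SAP 5.2.1 and 4.4.4:

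- First confirm that the pre-specified limit is meant as a 2- or 5-year cumulative incidence, and how it was derived.
- Base the tested estimate on 1 minus Kaplan-Meier for first AEI at Day 731 and Day 1826, separately for nodule/papule and for other AEIs. Censor event-free subjects at last follow-up and compare the confidence limit with the pre-specified limit.
- Keep the present proportion as a labelled best-case bound.
- Keep multiple imputation and the completer analyses as sensitivity analyses, because Kaplan-Meier assumes uninformative dropout. Report the imputation result with a confidence interval.
- Align the synopsis and Protocol 13.7 with the new rule and list the change in SAP 6.0.

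Cost: no new data, and the SAP already plans Kaplan-Meier for first occurrence. Protocol 13.1 provides for SAP revision before database lock, but changing the rule in Protocol 13.7 is an amendment that needs FDA and IRB approval (Protocol 24). Interim results are reported from Month 13 in an open-label study, so the date and reason for the change should be recorded. The stated incidence will rise slightly. At 17.2% the 95% half-width grows from 1.96 × √(0.172 × 0.828/863) = 2.5 points towards at most about 3.0 points (n = 604).

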10 SUBJECT SAFETY

10.1 ADVERSE EVENTS MONITORING

Adverse events will be documented at each treatment and follow up visit, monthly safety contacts, and any unscheduled visits.

All adverse events will be managed and reported in compliance with all applicable regulations and will be included in the final clinical study report.

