12.2 MONTHLY SAFETY CONTACTS

During the follow-up phase (Month 3 through Year 5), the site personnel will contact each subject monthly to review/record adverse events that have occurred and relevant medication that were taken since the last site visit, as well as confirm the next follow-up visit. The monthly safety contact and reminder contact will occur at the same time, whenever possible. In the event an adverse event is recorded that is listed in Section 9.1.1 (Primary safety criteria), the subject will be brought in for an unscheduled visit.

Subject contact information should be reviewed and updated if needed. If the site is unable to contact the subject directly within 3 months before each of their annual follow-up visits, the site will attempt to make 3 attempts to contact the subject, followed by 2 certified letters.

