5.3 Relative Day Ranges and Visit Windows

If a subject discontinues early, the efficacy data (wrinkle assessments and investigator/subject global evaluations) from Visit 12 (Year 5) will be reassigned to a scheduled visit based on the relative ranges in the following table. If a result already exists for the calculated visit or the calculated visit was not a scheduled visit, the next scheduled visit will be assigned.

Relative day calculations will be the parameter visit date of interest minus the Study First Treatment Date plus one.

Table 1: Visit Collection Time and Relative Day Ranges

Collection Time (Target Day ± Visit Window)	Relative Day Ranges
Baseline (Day 1)	≤ Day 1
Week 3 (Day 22 ± 3 days)	Day 2 to Day 32
Week 6 (Day 43 ± 3 days)	Day 33 to Day 53
Week 9 (Day 64 ± 3 days)	Day 54 to Day 124
Month 6 (Day 184 ± 2 weeks)	Day 125 to Day 290
Month 13 (Day 397 ± 2 weeks)	Day 291 to Day 564
Year 2 (Day 731 ± 4 weeks)	Day 565 to Day 913
Year 3 (Day 1096 ± 4 weeks)	Day 914 to Day 1278
Year 4 (Day 1461 ± 4 weeks)	Day 1279 to Day 1643
Year 5 (Day 1826 ± 4 weeks)	≥ Day 1644

5.4 Calculation of Duration and Time to Onset:

Below are the rules on how duration and time to onset are calculated:

- 1. Duration = Event End Date Event Start Date + 1
 - For events that are ongoing, the formula will be updated per following scenarios:
 - a. If the subject had XXX visit, duration will be XXX visit date minus start date plus 1;
 - b. If the subject discontinued the study, duration will be discontinuation date minus event start date plus 1;

- c. If none of the above, the event's duration will be time of visit minus study day of event start date plus 1, where time of visit is defined as scheduled study day + 4 weeks (2 weeks for Month 13).
- 2. Time to Onset (from treatment) = Event Start Date Date of First Treatment.

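### SAP 5.2.2 and 5.2.3 impute partial start dates as early and stop dates as late as possible, with no bound from event-free visits, biasing onset early and duration long for affected events

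*SAP*

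**What the plan says.** SAP 5.2.3 imputes an incomplete start date from two reference dates only, first treatment and the imputed stop date:

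- Year missing: "If the year is missing, the start date will be imputed as the minimum of the Study First Treatment Date and the imputed stop date".
- Month missing, year different from the treatment year: "the start date will be set to January 1st of the given year".
- Month missing, treatment year, stop in another year: "the start date will be set to the date of first treatment". If the stop is in the same year, the earlier of first treatment and the imputed stop is used.
- Only the day missing, month other than the treatment month: "the start date will be set to the first day of the given month for the given year".

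SAP 5.2.2 works the other way. An incomplete stop date goes to the end of the known month or year, or to the final study date if the subject left before then. If the stop year is missing and the subject is still in the study, the event is treated as ongoing.

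These dates are then used directly. SAP 5.4 has "Time to Onset (from treatment) = Event Start Date" minus the date of first treatment, and takes duration from start to end. SAP 4.4.4.2 splits onset at 30 days (nodules and papules) or 120 days (other events of interest), splits duration at 30 days, and gives Kaplan-Meier estimates of both. SAP 4.4.6 includes events at each interim by start date.

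On data collection, Protocol 10.1 states: "Adverse events will be documented at each treatment and follow up visit, monthly safety contacts, and any unscheduled visits". Protocol 12.2 adds that from Month 3 to Year 5 "the site personnel will contact each subject monthly to review/record adverse events".

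**The concern.** Earliest-start dating is a sensible way to decide whether an event is treatment-emergent. It is a poor way to estimate when the event began. The visible SAP keeps no separate date for the second purpose, so a lesion that appeared late can be reported as starting on the day of treatment, even if a later visit found the subject free of it. Late stop dates stretch duration at the other end.

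Onset and duration are secondary safety results in a study set up to describe long-term and chronic reactions. The error runs one way: late lesions look early and short lesions look long. SAP 4.4.4.2 handles ongoing events in two ways, but no visible analysis tests the effect of imputed dates.

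**Working it through.** The plan states no figure for this point, so there is none to reproduce. The check applies the rules of SAP 5.2.2 and 5.2.3 literally to events with assumed true dates.

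**Inputs.** Pivotal-study medians (Protocol section 4): nodule onset 160 days, duration 100; papule onset 55, duration 110. Year 2 target Day 731 and Year 5 target Day 1826 (SAP 5.3, Table 1). Planned N = 863. In the pivotal study, new events after Month 13 occurred in 3 subjects. Calendar dates below are assumed.

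**1. Year missing, stop date known.** The start becomes first treatment, so reported onset is 0 and reported duration is true onset plus true duration.
- Nodule: 160 + 100 = 260 days instead of 100.
- Papule: 55 + 110 = 165 days instead of 110.

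Both move into the class of 30 days or less.

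**2. Month missing at both ends, treatment year.** First treatment 10 Feb 2016; nodule first recorded at about Month 9 (10 Nov 2016, 274 days after treatment); start and stop known only as 2016. The start becomes 10 Feb and the stop 31 Dec. Onset is 0 and duration 326 days.

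**3. Month missing, later year.** The start moves to 1 January: a shift of 182 days on average and 364 at most, if onset is uniform over the year.

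**4. Only the day missing.** The shift is at most 30 days, but that can cross the 30-day cut. First treatment 5 Mar; papule on 29 Apr (55 days), recorded as April. The imputed start is 1 Apr, which is 27 days. If Visit 3 (Day 43 = 16 Apr) was attended and clean, the imputed onset precedes a clean visit. Bounding the start at 17 Apr or later gives at least 43 days, in the correct class.

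**5. Two-year count.** First treatment 10 Feb 2016; event known only as 2018; first recorded in October 2018. From 10 Feb 2016 to 10 Feb 2018 is 731 days; 40 days back to 1 Jan 2018 leaves 691, which is relative Day 692. That is before Day 731, so the event counts as within 2 years.

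True onsets from Day 732 to Day 1826 span 1,095 days. With the month missing, those moved inside Year 2 are the ones in the calendar year of the second anniversary: on average about 182/1,095 = 17%, with a range of 0% to 364/1,095 = 33% by treatment date. With the year missing, all are moved. With only the day missing, about 1% are.

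Assume first onsets after Year 2 at 3/116 per year for 3 years: 863 × 3 × 3/116 = 67 subjects. Assume 1% to 10% of these have the stated part missing:

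| Missing part | Added to 2-year count | Percentage points of 863 |
|---|---|---|
| Month | 0.1 to 1.1 subjects | 0.01 to 0.13 |
| Year | 0.7 to 6.7 subjects | 0.08 to 0.78 |

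If late first onsets were 2% or 10% of subjects (17 or 86) and 10% lacked the year, the addition would be 1.7 or 8.6 subjects (0.20 or 1.00 points).

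**6. Five-year counts.** An in-study event moved earlier after treatment is still within 5 years. Nothing changes.

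**The case against.** The case for leaving the rule alone has four parts.

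- **Missing months or years should be rare.** Onset and resolution dates are CRF items (Protocol 9.1.1). Under Protocol 12.2 and 12.3, an event of interest brings an unscheduled visit, a photograph, monthly contacts and a visit to verify resolution or stabilization. Examples 1, 2 and 5 are therefore extremes. This stands. The day-only gap is more ordinary, and its shift is small.
- **Worst-case dating is consistent with the rest of the plan.** Unknown timing counts as treatment-emergent, missing intensity as most severe, and missing relationship as possible. Any shift in 2-year incidence is upward, which is conservative for safety. This stands for the flag and for incidence. It does not stand for onset, where early dating hides late lesions.
- **The Year 2 effect is limited.** The Year 2 data are locked after all subjects' Year 2 visits, so a later event can enter that analysis only if it was recorded before the lock. The subject must also have no earlier event of that class. The table above ignores both conditions, so it gives upper limits under its assumptions.
- **Event-free contacts may not be usable.** The protocol does not say that the date and negative result of a monthly contact reach the eCRF, and such a contact is not an examination. SAP 5.1 bars unscheduled visits from analysis. This stands, and it limits the bound to recorded visits unless contact status is captured.

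A reader might infer that the onset, duration and 2-year results will be wrong, or that the co-primary result is at risk. The documents support neither. The number of partial dates is unknown, and the 5-year counts are unaffected. SAP numbering also jumps from 5.2.3 to 5.2.5, so a further date rule in the unseen 5.2.4 cannot be excluded.

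**Conclusion.** The point holds for partly dated events. On the visible text, their onset is biased early and their duration long, and nothing stops an imputed date from contradicting a recorded clean visit. Per event, the shift is at most 30 days when the day is missing, up to 364 days under the 1 January rule, and the whole time since treatment when the year is missing. In aggregate the effect is probably small, because such dates should be few.

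The 2-year count could rise by 0.01 to 0.78 points on the assumed 67 late first onsets and 1% to 10% missingness; about 9 subjects (1% of 863) are needed for 1 point. Whether that could alter the Year 2 test cannot be computed, since its threshold is not visible. The co-primary endpoints are not at issue. This is a low-cost improvement to secondary safety results and does not threaten the trial's main conclusion.

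**What to change.** Keep SAP 5.2.3 for the treatment-emergent flag. For time to onset, duration and 2-year inclusion, add the following:

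1. Set the imputed start no earlier than the day after the last recorded visit without the event and no later than the date it was first recorded, within the known month or year. Use a monthly contact as a bound only where its date and adverse event status are captured; the sponsor should confirm whether they are.
2. Cap the imputed stop at the first visit recording resolution.
3. Make an exception in SAP 5.1 so that unscheduled visit dates can serve as bounds.
4. Report how many start and stop dates were imputed and which part was missing.
5. Show the present 5.2.3 dating as a sensitivity analysis.

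With monthly contacts captured, the nodule in step 1 would show onset 129 to 160 and duration 100 to 131, instead of 0 and 260. With visits alone the bound is wider, up to about a year between annual visits. A clean Year 2 visit is still enough to keep a later event out of the 2-year count, because SAP 4.4.6 cuts at that visit.

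The cost is SAP wording and some extra programming. Bounds stay wide where contacts were missed, and before Month 3, when monthly contacts have not begun.
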